Assumptions for Power Calculations. Assumptions are based on interpolated data since primary outcomes in our first ACU study were assessed with the PSS-SR scale and there are no PTSD studies using MIN as the sham. Furthermore, to be consistent with major PTSD research, we will use the CAPS-5 (DSM-5 version) as the primary outcome, and there are as of yet no completed clinical trials using CAPS-5. In our first study, mean pre-treatment PTSD severity score was about 62% of maximum (31.55 of 51). ACU mean decreased 50% - 31.33 (10.1) to 15.65 (13.95) and wait-list mean decreased 9.3% - 30.79 (9.54) to 27.92 (12.33) at post-treatment. We thus assume that subjects will have a baseline mean CAPS-5 score of 50 (10) and a 50% reduction of symptoms and a 38% increased variance (CAPS-5 = 25; SD = 13.8) with ACU. There are sparse data about effects of MIN, noting a 33% improvement compared to pharmacological treatment only, and a 33% less effect than ACU in the Shen study. A 2010 Cochrane systematic review of over 200 trials investigating 60 clinical conditions about general placebo effect found placebos to not have important clinical effects but may influence patient-reported outcomes in some situations (e.g., pain and nausea). The pooled relative risk calculated for placebo was 0.93 (effect of only 7%) but significant. Confidence intervals are generally wide in the placebo arm. Several clinical and methodological factors were associated with higher effects of placebo. Since our study

includes some of these factors, and since we expect MIN to have some physical effect, MIN could provide an effect as much as 33% with a wider variance. This would predict mean CAPS-5 scores (MIN) at end-treatment of 33.5 (SD 15). The conservative prediction is mean CAPS-5 reductions of 25 points with ACU and 16.5 points with MIN, an 8.5-point difference with a pooled SD of 14.4. Given our experience and data about placebo effect, we can modestly expect a 12 point between group CAPS-5 difference and a pooled SD of 15.

Treatment Effects, Power and Sample Size, Primary Hypothesis. “The efficacy of verum acupuncture (ACU) for PTSD symptom severity will be large (pre- to post-treatment Cohen’s $d \geq 0.8$), and significantly better than sham acupuncture (MIN) (between group Cohen’s $d \geq 0.30$, with 80% probability of detecting a true group difference at $p < 0.05$ (2-sided).”

Effects. The conservative assumptions noted above will result in pre- to post-treatment Cohen’s $d = 2.07$ within group (ACU) and between group (post-treatment difference) Cohen’s $d = 0.59$, which will prove the null hypothesis false and show a large treatment effect for ACU and a moderate between-group effect size.

Sample size needed and power. The conservative assumptions would require a total of 90 patients in a two-treatment parallel-design to provide a probability of 80 percent to detect a treatment difference at a two-sided 0.05 significance level. Modest assumptions of a 12-point difference with a pooled SD of 15 requires a total of 50 patients with power of 0.80 at $\alpha < 0.05$.

This was determined using a formula for a random effects modeling (Montgomery, 1991), which may determine the necessary sample size to detect a statistically significant difference in treatment/control group means at different levels of projected effect differences.

$$n = \frac{2 * a * M^2 * \Phi^{*2}}{\Delta^2}$$

Where:

M = measure of noncentrality parameter to estimate the standard normal probability of making a type II error

n = number of replicates necessary for each treatment

a = number of treatments (a=2)

Φ^* = estimated standard deviation

Δ = difference in baseline and post treatment

Table. Examples of sample sizes necessary for significance testing at different mean and SD’s (between group: treatment (ACU) and control (MIN)) for PTSD severity (primary outcome) at power = 0.80.

Mean difference between ACU and MIN PTSD severity scores post-treatment	Φ^2	Total N Using Formula Above
8.5	12	62
	14.4	90
	15	96
	20	162
12	12	32
	15	50
	20	86

Recruitment goals are N=90, 45 per group. With a post-randomization attrition rate of 10% we will have at least 40 individuals in each group. Considering attrition, the above table indicates that for an average difference in means of 12 at end-treatment with a standard deviation of 15, a total sample size of 50 (25 in each group) would be more than adequate to report a statistical difference with 80% power. If differences in treatment group means were found to be larger than 12, we would need even fewer subjects in our treatment groups to achieve statistical significance.

PPR Data Recording and Reduction. A description of the procedure/data is in [Appendix 4](#). Data reduction and analyses will follow current established protocols in our lab (Norrholm et al, 2011a). Data will be collected with the BioSemi recording software (BioSemi B.V, Amsterdam, Netherlands) and the resulting data will be exported to Mindware software (Mindware Technologies LTD, Gahanna, OH) for data reduction and generation of analyzable variables.

Startle data reduction for analyses. The raw EMG signal will be recorded at a rate of 1000 Hz throughout the experimental session using a 28 Hz high pass and 500 Hz low pass filter (as recommended by guidelines for human eyeblink startle in Blumenthal et al., 2005; *Psychophysiology*, 42:1-15). Raw signals will be stored and exported for analysis in microvolt (μV) values.

Skin Conductance Response. Skin conductance responses are scored as the largest amplitude responses beginning in a window of 1 to 3 seconds following stimulus onset. A response is defined as having amplitude greater than 0.01 μS relative to the pre-stimulus baseline (Boucsein et al, 2012).

Heart rate. Average heart rate (HR), the standard deviation of the HR, power of high frequency (HF), low frequency (LF), very low frequency (VLF) components, % power of LF (%LF [of VLF+LF+HF]) and of HF (%) and the ratio of the LF over the HF (LF/HF ratio is used as an indirect autonomic balance index) of HRV are calculated as cardiac activity measures. Artifact-corrected 3-min long recording epochs are analyzed with FFT to assess HRV. Inter-beat Intervals (IBIs) will be scored as the time difference between successive R waves in the ECG signal. IBIs will be used as the dependent variable analyzed instead of heart rate because of a lowered susceptibility to artifact due to differences in baseline values (Stern et al., 2001). A window of 3 seconds pre-stimulus onset to 6 following stimulus onset will be scored. Instantaneous IBIs will be recorded at half-second intervals during the pre- and post-stimulus time windows. A difference score between the average pre-stimulus IBI for each trial and each post-stimulus IBI value will be computed for each trial. IBIs will later be converted heart rate (beats per minute) for more readily interpretable post-analytic write-ups.

Respiration. Respiration will be scored in a similar fashion to the ECG data and reported in interbreath intervals. Peak detection of each positive deflecting curve in the breathing cycle will be manually reviewed visually to assess accuracy. Interbreath intervals will later be converted to respiration rate (breaths per minute) for ease of interpretation.

Clinical Protocol Detail

Interventions. All subjects will be allocated to intervention group by a computer-generated adaptive randomization procedure. Selected participants will go through a preliminary phase to assess if there are specific acupuncture points that change heart rate and heart rate variability more than others during the psychophysiology assessment.

Group 1 will receive verum acupuncture (ACU) (experimental intervention) delivered in 1-hour sessions, twice per week for 12 weeks.

Group 2 will receive minimal acupuncture (MIN) (sham placebo control), also delivered in 1-hour sessions, twice a week for 12 weeks.

Subjects will be blinded to intervention (i.e., if experimental or sham). Clinical assessor(s) and investigators will be blinded to randomization. The acupuncturist cannot be blinded, and so will follow a standardized protocol to minimize intervention bias and treatment fidelity will be assessed.

Maintaining Blind and Non-specific Treatment-related Effects

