Recruitment. A two-stage detection method will be utilized to identify a sample of PTSD treatment seekers. Based on our previous study, we expect a 15% drop-out rate prior to the start of intervention; these will be replaced. Subjects who withdraw after starting treatment will not be replaced: based on our previous study we expect a 10% rate. This would leave 40 in each intervention group for a treatment completion analysis. Data of subjects who withdraw at any time after randomization will be retained for intent-to-treat analyses.

Stage I: Screening for Inclusion/Exclusion. The PM/RA will contact potential subjects and ask them to provide written informed consent for study screening. Those who consent will be assessed with screening questions for inclusion and exclusion criteria, availability, and willingness to participate in the study. This visit may be conducted in person or by phone and will take about 20 minutes.

Stage II: Inclusion Confirmation. The assessor will administer The CAPS-5, a modified Structured Clinical Interview for Diagnosis DSM-5 (SCID-5, now modified) (First et al, 2001), and the Dissociative Experiences Scale-II (Bernstein & Putnam, 1985) to assess inclusion and exclusions and further assess willingness and capacity to participate (i.e., have time and motivation). The Deployment Risk and Resiliency Inventory (DRRI) combat experiences scale and preparedness scale (Vogt et al, 2008) will be administered to aid group allocation. The study PI will assess current medications as potential exclusions. This visit will take about 2 to 3 hours.

After confirmed inclusion, the PM will reiterate the schedule, group allocation and compensation, and obtain written informed consent for participation. This will include informed consent to be videotaped to assess treatment fidelity. All hard and electronic data forms will be identified only by SID#. The clinical assessor will assess participants at each time point blind to group allocation. This procedure will keep the assessor blind to intervention allocation, and investigators and clinicians blind to assessment data to minimize performance and outcome detection bias.

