Data collection. The program manager (PM) will track recruitment and retention. A clinical assessor will conduct diagnostic interviews and questionnaire evaluations pre-, mid-, and post-intervention blind to group allocation. All pre-, mid-, and post-treatment biological measures will be conducted and analyzed by the psychophysiological and consultants, blind to group allocation.

Assessment, Data Collection, and Schedule. Instruments and other data collection tools and their description are in the [Assessment Detail](#). This strategy includes repeat measures yet minimizes response burden. Our goal is to test for effect signal. It is premature to evaluate durability and not ethical to keep subjects in a protocol where they may not be receiving effective treatment (particularly true of MIN), so we will not include a six-month follow-up period. Instead, a one-month follow-up will test symptoms and functioning and be utilized to re-connect participants to clinical services. Data collection at mid-point of treatment is warranted to replicate mid-treatment findings from our first trial. Such a finding may help determine dose effects and plan a dose-finding trial.

Outcome measures. The primary outcome is change in PTSD symptom severity from pre- to post-treatment. We hypothesize a large pre- to post-treatment effect for ACU ($d \geq 0.8$) and at least a mild treatment effect ($d \geq 0.30$) of the difference between groups (ACU vs MIN) pre- to post-treatment, with 80% probability of detecting a true group difference at $p < 0.05$ (2-sided). Main biological outcome (secondary outcome) is change from pre- to post-treatment in PPR (decreased startle by EMG eyeblink).

IV. Statistical Plan and Data Analyses

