General Approach. General linear mixed models (GLMM) are capable of handling multiple underlying distribution and model structures through link functions, such as repeated measures random effects models of continuous outcomes (identity link), repeated measures logistic models (logit link), and Poisson and negative binomial models (log link). In addition to modeling global fixed effects across subjects, GLMM can also model individual subject random effects. Survival analysis allows for the assessment of time to event modeling using probability estimates on survivor functions and estimates of hazard ratios. Time to event modeling using Cox proportional hazard modeling allows for all subjects to contribute information to the model up until occurrence of event, drop out, or end of study. Cox Proportional Hazards modeling will be used to investigate for effect-size of the treatment by allowing subjects to contribute their information to the model while they are being observed and censored once they are no longer being observed (loss to follow-up or end of study period). Further, using the Cox modeling we will investigate for time dependencies and informative loss to follow-up. In the case where dropouts may be associated with the treatment assignments, we will leverage intention to treat methodology and construct a piecewise random effects model with both "on-" and "off-treatment" slopes. GLMM will be used to evaluate the primary clinical hypothesized effects of treatment (ACU) on the clinical outcome of PTSD symptom severity (CAPS) over time (mid- and end-treatment, and 1-month follow-up), controlling for baseline severity of symptoms and demographic characteristics (e.g., age, gender) in comparison with placebo control group (MIN) with assumption of intent to treat. Cohen's *d* within and between subjects will be calculated. Interaction terms will be included in the models to evaluate treatment fidelity and treatment expectancy as potential moderators.

GLMM will also be used to evaluate the secondary biological hypothesized effects of treatment on pre- to post-treatment in PPR (decreased EMG eyeblink). These same statistical procedures (GLMM, survival analysis, and Cohen's *d* with intent to treat) will be applied to evaluate exploratory outcomes: clinical symptoms comorbid with PTSD, PPR (HR, HRV, SCR), and PTSD diagnosis.

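### The primary hypothesis ties 80% power to a between-group d of 0.30 or more, but N = 90 was sized for d = 0.59 and gives about 29% power at 0.30

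*Protocol*

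**What the plan says.** **Hypothesis.** Protocol section III, Data Management (Outcome measures), hypothesises at least a mild between-group effect and continues: "d \geq 0.30$) of the difference between groups (ACU vs MIN) pre- to post-treatment, with 80% probability of detecting a true group difference". The quoted primary hypothesis in section IV has the same pairing, "d \geq 0.30$, with 80% probability of detecting a true group difference at $p < 0.05$ (2-sided"), and the SAP repeats it under Treatment Effects, Power and Sample Size, Primary Hypothesis.

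**Sample size.** The next paragraphs use a different effect. An 8.5-point CAPS-5 difference with pooled SD 14.4 is given as "d = 0.59$, which will prove the null hypothesis false". From this follows: "The conservative assumptions would require a total of 90 patients in a two-treatment parallel-design to provide a probability of 80 percent". The only other case discussed in the text is 12 points with SD 15, needing 50 patients. Neither document has a calculation for d = 0.30.

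**Attrition.** Recruitment is 45 per group, with 10% loss expected after treatment starts: "This would leave 40 in each intervention group for a treatment completion analysis". The sentence on adequacy after losses covers only the more favourable case: "Considering attrition, the above table indicates that for an average difference in means of 12 at end-treatment with a standard deviation of 15".

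**Analysis model.** The mixed model for the primary outcome is planned as "controlling for baseline severity of symptoms and demographic characteristics". No baseline-to-post correlation is given, and the sample size calculation takes no credit for one.

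**The concern.** One power figure is attached to two effects that differ about twofold. A claim of 80% power for every d of 0.30 or more has to hold at 0.30, and the calculation supports it only from about 0.60 upward.

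This affects how the main result will be read. Anyone relying on the hypothesis statement would take a null result as fairly good evidence against effects down to 0.30. In an unadjusted comparison the trial would miss a true effect of that size about 7 times in 10. The protocol's Participants and sampling paragraph also calls 90 adequate for the primary hypothesis without naming the effect for which that is true.

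**Working it through.** **Inputs from the documents.** Two-sided alpha 0.05; power 80%; 1:1 allocation, 45 per arm; difference 8.5 points; SDs 13.8 (ACU) and 15 (MIN); at least 40 per arm after 10% attrition; hypothesised between-group d of at least 0.30.

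**1. Reproduce the plan's N.**
- Pooled SD = √((13.8² + 15²)/2) = 14.41. d = 8.5/14.4 = 0.590.
- Normal approximation: total N = 4 × (1.960 + 0.842)² × SD²/Δ² = 4 × 7.849 × 14.4²/8.5² = 90.1.
- The plan's 90 is therefore correct for d = 0.59.

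**2. Unadjusted power.** The noncentrality is d × √(n/2), with n per arm.

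| True effect | 45 per arm, t (normal) | 40 per arm, t (normal) |
|---|---|---|
| d = 0.30 | 29% (30%) | 26% (27%) |
| 8.5/14.4, d = 0.59 | 79% (80%) | 74% (75%) |
| 12/15, d = 0.80 | 96% (97%) | 94% (95%) |

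**3. N needed for d = 0.30.** 4 × 7.849/0.30² = 348.8, so about 350 patients (352 by t-test). The plan's own table points the same way. Its smallest effect, 8.5/20 = 0.425, is listed as needing 162 patients, so a smaller effect cannot need only 90.

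**4. Smallest d with 80% power (t-test).**
- 45 per arm: 0.597, or 0.597 × 14.4 = 8.6 points (0.591 by the normal formula).
- 40 per arm: 0.634, or 9.1 points.
- For comparison, 0.30 × 14.4 = 4.3 points.

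**5. Credit for baseline adjustment.** With baseline-to-post correlation r, the effective d is d/√(1 − r²), on 2n − 3 degrees of freedom. Every r here is an assumption.

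| d = 0.30 | r = 0.3 | r = 0.5 | r = 0.7 | r = 0.8 |
|---|---|---|---|---|
| 45 per arm | 31% | 37% | 50% | 65% |
| 40 per arm | 28% | 33% | 46% | 60% |

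80% power at 0.30 requires r = √(1 − (0.30/0.597)²) = 0.86 with 45 per arm, or √(1 − (0.30/0.634)²) = 0.88 with 40.

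**6. The 8.5-point case after attrition.** With 40 per arm and adjustment, power is 78%, 81% and 85% at assumed r of 0.3, 0.4 and 0.5. It reaches 80% at r of about 0.37.

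**The case against.** **The 0.30 is only a hypothesised floor.** On this reading the 80% belongs to the 0.59 that follows, and the sizing basis is disclosed openly and computed correctly. That may well be the intent, and a careful reader of the power section can find it. But the hypothesis statements do not say it, in either document. If it is the intent, the rewording below simply states it.

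**The two d values may be on different scales.** The Outcome measures paragraph describes a pre- to post-treatment difference, while 0.59 is a post-treatment difference. This stands in part. The 4.3-point translation holds only if 0.30 is standardised by the post-treatment SD of 14.4. The 29% does not depend on it: an unadjusted two-group test at d = 0.30 has that power on whichever scale defines d.

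**The planned model uses several visits.** Suppose the effect is constant over the mid-treatment, end-treatment and 1-month assessments, with baseline correlation r of 0.3 to 0.5 and between-visit correlation ρ of 0.6 to 0.7 (all assumed). The variance factor for the visit average is (1 + 2ρ)/3 − r², from 0.71 (r = 0.3, ρ = 0.7) to 0.48 (r = 0.5, ρ = 0.6). Dividing 0.30 by its square root gives an effective d of 0.356 to 0.432, and power of 39% to 53% with 45 per arm. That is still far from 80%, and the primary outcome is the pre- to post-treatment change, not the visit average.

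**Attrition is overstated.** Withdrawals before intervention are replaced, all randomised data are kept for intent-to-treat, and the 40 per arm is described for a completer analysis. This is fair. The 74 to 75% is an unadjusted completer figure, and modest baseline adjustment would restore 80%. The attrition point is therefore a disclosure gap only.

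**The remedy leaves the power unchanged.** True, but the error is in what the plan claims for its power. Correcting the claim is the appropriate remedy.

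**Conclusion.** The concern holds and should be corrected. N = 90 is right for d = 0.59 by the plan's formula, but the 80% stated alongside d of 0.30 or more is wrong. Unadjusted power at 0.30 is about 29% with 45 per arm and 26% with 40. Under assumed correlations of 0.3 to 0.7, baseline adjustment raises the 45-per-arm figure to between 31% and 50%, so a true effect of 0.30 would be missed about 5 to 7 times in 10. The unadjusted figures rest only on the documents' numbers; the adjusted ones rest on correlations that the documents do not give.

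The attrition point is secondary and does not drive this conclusion. The 12-point sentence is true (94% with 40 per arm), but it does not address the 8.5-point case that set N.

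**What to change.** 1. In the protocol's Outcome measures paragraph, and in the primary hypothesis in protocol section IV and the SAP, detach the 80% from d of 0.30 or more. Keep 0.30, if wanted, only as a descriptive minimum. Add:

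> In an unadjusted comparison, N = 90 (45 per arm) has about 80% power for d of about 0.60 (8.6 CAPS-5 points at SD 14.4; t-test) and about 29% at d = 0.30.

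   Naming the t-test explains the small difference from the plan's 0.59 and 8.5 points, which come from the normal formula.

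2. In both documents, keep the 12-point sentence after the sample size table and add:

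> Unadjusted and with 40 completers per arm, power for 8.5 points is about 74 to 75% (detectable d 0.63).

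3. If credit is taken for the baseline-adjusted intent-to-treat model, state the assumed baseline-to-post correlation and the resulting power.

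4. Let the general statement that 90 is adequate, under Participants and sampling, name the effect it refers to.

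The cost is wording in the protocol and SAP, with no change to N, test or analysis. The only downside is a less favourable stated power.
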